5.2 Secondary Endpoints

- Proportion of participants with Serious Device and/or Serious Procedure-Related AEs from initial ELS Treatment through 30 days following last ELS treatment.
- Proportion of participants with Serious Device and/or Serious Procedure-Related AEs from initial ELS Treatment through 90 days following last ELS treatment.
- All AEs & SAEs from initial ELS Treatment through 30 days following last ELS treatment
- All AEs & SAEs from initial ELS Treatment through 90 days following last ELS treatment
- Participant satisfaction at 30 day follow-up following last ELS treatment

5.3 Other Observations

- Pain scores will be summarized and tabulated by visit, including subgroups of participants with pain versus no pain at baseline.
- Use and quantity of pain medication for managing stone-associated pain will be characterized by timing and type of medication.
- Proportion of participants who underwent various anaesthesia regimens (e.g. general/local)
- Procedural data will be tabulated
- Length of hospital stay
- Stones that are retained will be characterized

6. STUDY VISIT SCHEDULE AND PROCEDURES

6.1 Screening

Screening for this study includes the following assessments. Refer to the Schedule of Assessments Table 2: Schedule of Events.

Confidential

Page 15 of 19

Study of an Enhanced Lithotripsy System in the Treatment Of Urinary Stone Disease (STONES)

Version 2.0, July 10, 2019

- Participants will undergo a CT scan within 14 days of the ELS procedure to estimate the approximate stone size (in mm), radiodensity and location (e.g. renal pelvis, distal ureter). Investigators should perform additional imaging prior to ELS treatment, particularly if symptoms have changed or if a participant is in the process of ureteral stone passage, because a change in stone position may influence treatment approach. This additional imaging can include KUB x-ray, renal/bladder US, or CT depending on investigator's discretion. If CT imaging is performed more than once, the CT imaging that occurs just prior to the first ELS procedure will be counted as baseline.
- The scout film acquired during the baseline CT is recommended to be used to document radiopacity for participants suspected with radiolucent stone(s). A KUB x-ray may be performed if the scout film is not available for this purpose.
- Participants will undergo a physical exam and medical history.
- For women of child-bearing age, participants will undergo a pregnancy test (if necessary).
- Participants will undergo a urinalysis and urine culture.
- Serum creatinine will be collected to review renal function.
- Prior to treatment, participant usage of pain medication (type, dose and frequency) will be documented, whether such pain medications were prescribed in connection with the scheduled study procedure or otherwise.
- Prior to treatment, participant usage of anticoagulants (type, dose and frequency) will be documented.
- Within 1 day of the ELS Treatment, study participants will also be asked to complete a pain questionnaire (pain score). The pain questionnaire may be completed on the same day as ELS Treatment before the treatment takes place.

6.2 Study Visits

Refer to Table 2: Schedule of Events.

6.2.1 ELS Treatment

The investigator and designated co-investigator(s) will be trained to the IFU before performing the investigational procedure (ELS treatment). Refer to the IFU for a complete description of the ELS treatment procedures.

ELS Treatment is expected to take between around 30 minutes and around 60 minutes, depending on stone size. Additional time may be required before and after treatment. The procedure will be performed using local anaesthesia and light or moderate sedation, or a light general anaesthesia as per investigator discretion, local regulations and standard clinical practice. During treatment, study participants will be monitored for clinically significant dysrhythmia (i.e. cardiac arrhythmia seen on ECG) herein defined as any alteration in cardiac rate and/or rhythm that necessitates directed intervention including the administration of antiarrhythmic agents, cardioversion, defibrillation, and/or physical manipulations such as vagal maneuvers.

The ELS treatment steps are described in detail within the IFU. Investigators are trained to the IFU before ELS Treatment.

At investigator's discretion or as directed by IFU, fluoroscopic or diagnostic ultrasound imaging may be used. Imaging that is used to document status of the stone, urinary tract, an adverse event or device deficiency shall be recorded and collected by research staff.

Upon completion of ELS Treatment, remove the 5 Fr catheter and initiate standard retrograde pyelogram recovery and discharge procedures.

AEs will be recorded.

6.2.2 Discharge

Study participants will follow the site-specific discharge procedure.

Study participants will be educated on methods for straining and collecting stone fragments. Following the procedure, they will be given a jug and sieve for straining their urine, an instruction sheet and a collection kit. They will be advised how to filter their urine, dry any collected stone fragments and store these fragments until directed to take back to their next clinic or doctor's appointment.

6.2.3 Follow-up at Days 1, 2 and 3

On Day 1, Day 2 and Day 3 post-procedure, follow-up visits will be conducted by phone (at a minimum).

- AEs since last observation will be documented (see Adverse Events section).
- Ensure participant is collecting any stone fragments obtained through urine straining.
- Ask about usage of pain medications (type, dose and frequency), whether such pain medications were prescribed in connection with the procedure or otherwise.
- Complete pain questionnaire (pain score) on Days 1, 2 and 3

6.2.4 Follow-up at Day 7 (7 days +/- 1 day after each ELS procedure)

Day 7 follow-up will be conducted by phone.

- Document any reported AEs since last observation was performed (see Adverse Events section below).
- Ensure participant is collecting any stone fragments obtained through urine straining.
- Ask about usage of pain medications (type, dose and frequency), whether such pain medications were prescribed in connection with the procedure or otherwise.
- Complete pain questionnaire (pain score).

6.2.5 Follow-up at Day 14 (14 days +/- 4 days after each ELS procedure)

- The participant will undergo a physical examination.
- The following imaging will be performed to observe the status of the ureter and stone:
 - Collect a KUB X-ray
 - Perform a renal bladder ultrasound to evaluate status of ureter and stone or residual fragments (if any).

Per investigator discretion, a low-dose, non-contrast CT to evaluate status of ureter and stone or residual fragments (if any) may be performed instead of the combination of X-ray and ultrasound.

- Document any reported AEs since last observation was performed (see Adverse Events section below).
- Collect and label any stone fragments obtained by the participant through urine straining.
- Urinalysis, including urine culture
- Ask about usage of pain medications (type, dose and frequency), whether such pain medications were prescribed in connection with the procedure or otherwise.
- Complete pain questionnaire (pain score).
- ELS Treatment eligibility will be assessed by the investigator. If the remaining stone size is 3 mm or more in any dimension, the participant is eligible for one additional ELS Procedure. Refer to Section 6.2.8.

6.2.6 30-day follow-up (30 +/- 4 days after each ELS procedure)

- Participants will undergo a low-dose non-contrast CT scan to assess ureter, stone (residual fragment) size, location and radiodensity (if stone/fragment present).
- Conduct an on-site follow-up after the last ELS treatment: 1) 30 days after first ELS treatment, if first treatment was successful, or 2) 30 days after second ELS treatment, if a second treatment was performed.
- Conduct focused physical exam
- Serum creatinine to assess renal function
- Document any reported AEs since last visit (see Adverse Events section below).
- Complete pain questionnaire (pain score) and document any pain medications
- ELS Treatment eligibility will be assessed by the investigator. If the remaining stone size is 3 mm or more in any dimension, the participant is eligible for one additional ELS Procedure. Refer to Section 6.2.8.

6.2.7 90-day follow-up (90 +/- 21 days after last ELS procedure)

Conduct an on-site follow-up after the last ELS treatment.

- Conduct focused physical exam
- Serum creatinine to assess renal function
- Perform diagnostic renal-bladder ultrasound to assess ureter.
- Document any reported AEs since last visit (see Adverse Events section below).
- Document concomitant medications

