4.3 Eligibility Criteria

4.3.1 Inclusion Criteria

1. Participant is ≥ 18 years
2. Participants has voluntarily signed/dated the informed consent form.
3. Participant understands and accepts the study requirements.
4. Participant has one urinary stone eligible for treatment (minimum) that is:
 - a. apparent on a computed tomography (CT) scan within 14 days prior to study enrollment,
 - b. located within the renal pelvis or ureter, and,
 - c. is ≥ 3 mm in all dimensions
 - d. is ≤ 10 mm in maximum dimension and has area $<56 \text{ mm}^2$, as estimated by pre-procedure CT (area calculation: product of mathematical constant pi and the square of the radius for a stone appearing approximately circular on CT; product of long dimension and short dimension for a stone appearing oblong on CT)
5. Participants with additional stone(s) in one or both kidneys are admissible and must meet the following inclusion criteria:
 - a. Number of stones (≥ 3 mm) present on treated side is 2 or less
 - b. Untreated stones must not be anticipated to require treatment within 30 days of enrollment, as determined by the investigator

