4.4.4 Point of enrollment

Enrollment is defined as that time when the participant signs the informed consent form and is then eligible to begin screening assessments. Participants who fail to meet screening assessment requirements (see Section 6.1) will be counted as a screen failure and will not be treated with the ELS. Screen failures will be documented at the site on a screening log.

Each enrolled study participant will be assigned a unique participant identification number at the time of enrollment. This participant identification number will be retained throughout the study. Investigational site will keep a log that notes the participant's name and corresponding participant identification number. All electronic case report forms (eCRFs) will be tracked, evaluated, and stored using only the participant ID number. No personal identifying information will be included on the eCRFs.

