6.3 Additional ELS Procedure

6.3.1 Eligibility

The participant may require an additional ELS Treatment of the urinary stone to meet the treatment success definition. Participants are eligible for retreatment if he or she meets the eligibility criteria (Section 4.3). The eligibility assessment will be performed at the Day 14 Follow-up and may be confirmed at the Day 30 Follow-up CT scan. The investigator shall document the circumstances that lead to participants that are eligible for an additional ELS

Treatment but decline, or based upon the investigator's discretion, are not suitable for an additional ELS Treatment.

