6.4 Non-ELS Treatment stone interventions

Participants may require intervention other than ELS Treatment to resolve their condition as it relates to their urinary stone(s) selected for ELS Treatment. This study requires one additional ELS Treatment to be performed if needed, as discussed in the section above. These additional stone interventions will be recorded on the appropriate eCRF. Adverse events will be assessed using the definitions in Section 8.1.

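### The retreatment size rule is stated in two ways: any dimension of 3 mm or more (6.2.5, 6.2.6), or the Section 4.3 criteria, whose item 4c requires 3 mm in all dimensions (6.3.1)

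*Combined protocol and SAP*

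**What the plan says.** The combined protocol addresses eligibility for the second treatment in several places.

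- **6.2.5 (Day 14) and 6.2.6 (Day 30):** "If the remaining stone size is 3 mm or more in any dimension, the participant is eligible for one additional ELS Procedure". Both then refer the reader to 6.2.8, which is Study Exit. The section on the additional procedure is 6.3.
- **6.3.1:** "Participants are eligible for retreatment if he or she meets the eligibility criteria (Section 4.3"). The same section gives the purpose of the second treatment: a participant "may require an additional ELS Treatment of the urinary stone to meet the treatment success definition".
- **4.3.1, item 4:** the qualifying stone must be "apparent on a computed tomography (CT) scan within 14 days prior to study enrollment" (4a) and must be one that "is ≥ 3 mm in all dimensions" (4c).
- **Synopsis, Treatment 2:** two conditions are joined. The treated stone or fragment is at least 3 mm (no dimension named), and the participant is still eligible under the inclusion and exclusion criteria.
- **Table 2, footnote 2:** the procedure is repeated for remnants of 3 mm or more on CT (no dimension named).
- **6.4:** "This study requires one additional ELS Treatment to be performed if needed".
- **5.1 and 11.3:** success after up to two treatments means no stone, or fragments below 3 mm in the largest dimension.

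**The concern.** The visit instructions and the primary endpoint both turn on the largest dimension of the remnant. Item 4c turns on the smallest. Section 6.3.1 brings item 4c into the retreatment decision by citing Section 4.3 as a whole, with no exception for stone size.

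The two rules disagree for remnants that measure 3 mm or more in one direction and less in another. These participants have failed the endpoint and are among those the second treatment is meant to help. A site that took 6.3.1 literally would withhold that treatment and leave them as failures of an endpoint defined after up to two treatments. Up to eight sites are planned, and they could apply the rule differently. At stake are some power and a clear treatment rule.

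**Working it through.** **1. The two rules side by side.** Let L be the largest and S the smallest dimension of the remnant.

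| Remnant | Endpoint (success if L < 3 mm) | 6.2.5/6.2.6 (L ≥ 3 mm) | 6.3.1 with 4c re-applied (S ≥ 3 mm) |
|---|---|---|---|
| 2 x 2 mm | success | not eligible | not eligible |
| 4 x 2 mm | failure | eligible | barred |
| 4 x 4 mm | failure | eligible | not barred by 4c |

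Only the middle row conflicts, that is L ≥ 3 mm with S < 3 mm.

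**2. The plan's own figures (11.6).** The inputs are performance goal 0.50, expected success 0.68, n = 58, and success declared at 37 or more.

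- The exact lower 95% limit is 0.501 for 37/58 (the protocol gives 0.502) and 0.484 for 36/58. The threshold of 37 is confirmed.
- P(X ≥ 37 | n = 58, p = 0.50) = 0.024.
- P(X ≥ 37 | n = 58, p = 0.68) = 0.7975, against a target of 80%.

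**3. Illustration of lost power.** The documents give none of the following, so all are assumptions:

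- f = share of participants whose remnant falls in the conflicting class
- s = success rate of a second treatment in them
- q = share of them at sites applying the strict reading
- the planned 68% presumes that they are retreated

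Then p = 0.68 − f × s × q, and power = P(X ≥ 37 | 58, p). For example, f = 0.02, s = 0.70 and q = 0.25 give p = 0.68 − 0.0035 = 0.6765 and power 0.781.

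| f | q | p (s = 0.30 / 0.70) | Power (s = 0.30 / 0.70) |
|---|---|---|---|
| any | 0 | 0.680 | 79.8% |
| 0.01 | 0.25 | 0.67925 / 0.67825 | 79.4% / 78.9% |
| 0.01 | 1 | 0.677 / 0.673 | 78.3% / 76.3% |
| 0.02 | 0.25 | 0.6785 / 0.6765 | 79.0% / 78.1% |
| 0.02 | 0.5 | 0.677 / 0.673 | 78.3% / 76.3% |
| 0.02 | 1 | 0.674 / 0.666 | 76.8% / 72.6% |
| 0.05 | 0.25 | 0.67625 / 0.67125 | 78.0% / 75.4% |
| 0.05 | 1 | 0.665 / 0.645 | 72.1% / 60.3% |

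The affected participants number 0.01 × 58 = 0.6, 0.02 × 58 = 1.2 and 0.05 × 58 = 2.9. The 60.3% figure stacks every unfavourable assumption.

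**4. Type I error.** The test compares the observed count with 37. When the true success rate under whichever rule is applied equals 0.50, the rejection probability is 0.024. The retreatment rule changes the true rate, not this probability or the threshold.

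**The case against.** The strongest reply is that the protocol, read as a whole, already favours the lenient rule.

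- Sections 6.2.5 and 6.2.6 are the specific instructions for the visits where the decision is made. Section 6.3.1 is a general back-reference.
- The synopsis lists fragment size separately from continuing eligibility. If 4c applied to the remnant, the separate size condition would be redundant. Continuing eligibility then reads naturally as participant-level status such as pregnancy, infection or anticoagulation.
- Item 4a is tied to enrolment, and "Enrollment is defined as that time when the participant signs the informed consent form". Item 4 can hardly be re-run on a Day 14 or Day 30 remnant and is better read as already met by the index stone.
- The purpose stated in 6.3.1, together with 6.4 and footnote 2, points the same way.

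Most of this stands. It makes the strict reading the less likely one, and nothing in the documents shows that any site would adopt it. It does not remove the conflict: 6.3.1 cites Section 4.3 without exception, and the synopsis condition on continuing eligibility can be read to support the strict rule. It also stands that the power figures rest wholly on assumed inputs, and that refusal or investigator discretion (6.3.1) would leave some participants without a second treatment under either rule.

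A reader might go further in three ways that the documents do not support.

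- That the protocol does deny these participants retreatment. It does so only on one literal reading, against the visit instructions.
- That item 5a ("Number of stones (≥ 3 mm) present on treated side is 2 or less") bars a participant whose stone broke into three pieces of that size. This needs the same re-application of enrolment criteria and is speculative.
- That footnote 2 is wrong to name CT. Section 6.2.5 permits CT at Day 14, and 6.3.1 allows eligibility to be confirmed on the Day 30 CT.

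**Conclusion.** The concern holds as a conflict between two stated rules. A remnant of 3 mm or more in its largest dimension but under 3 mm in its smallest is an endpoint failure, eligible under 6.2.5 and 6.2.6, and barred by 6.3.1 taken literally. On that reading 6.3.1 works against its own stated purpose.

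Any effect is towards lower observed success, so it costs power and cannot favour the device. The loss cannot be derived from the documents and is nil if all sites follow the visit instructions. Under the assumptions above with 2% affected, it is about 1 to 2 percentage points if a quarter of affected participants are at strict sites, and about 3 to 7 points if all are. Planned exact power is already just under 80%, so there is no reserve.

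A reader might infer that the sample size, the 37/58 threshold or the Type I error is wrong. None of these follows. This is a wording change worth making, not a threat to the validity of the primary test.

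**What to change.** In 6.3.1 and in the synopsis entry for Treatment 2, state that:

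- the size criterion for retreatment is a residual stone or fragment of 3 mm or more in its largest dimension, matching the primary endpoint and 6.2.5/6.2.6;
- items 4a (CT before enrolment) and 4c (3 mm in all dimensions) are not re-applied to the remnant;
- the exclusion criteria are re-checked before the second treatment.

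Changing the cross-reference in 6.2.5 and 6.2.6 from 6.2.8 to 6.3 is clerical and can go in the same edit.

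The cost is protocol wording and a clarification to sites, with no extra participants. Anyone who would otherwise have been refused has a second procedure, with the Day 1, 2, 3, 7, 14 and 30 visits and Day 30 CT already planned for it. At the assumed 1% to 5% affected, that is at most about 1 to 3 of 58 participants, even if every site had been strict.

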6.2.8 Study Exit

- Complete study exit form

6.3 Additional ELS Procedure

6.3.1 Eligibility

The participant may require an additional ELS Treatment of the urinary stone to meet the treatment success definition. Participants are eligible for retreatment if he or she meets the eligibility criteria (Section 4.3). The eligibility assessment will be performed at the Day 14 Follow-up and may be confirmed at the Day 30 Follow-up CT scan. The investigator shall document the circumstances that lead to participants that are eligible for an additional ELS

Treatment but decline, or based upon the investigator's discretion, are not suitable for an additional ELS Treatment.

6.3.2 Scheduling

The additional ELS Treatment is recommended to be performed 30 days (\pm 14 days) from the index procedure (Day 0). When an additional ELS Treatment is performed, participants will repeat the Day 1, 2, 3, 7, 14 & 30 follow-up visits. The Day 90 Follow-up visit is expected to occur 90 +/- 21 days from the last ELS Treatment.

6.4 Non-ELS Treatment stone interventions

Participants may require intervention other than ELS Treatment to resolve their condition as it relates to their urinary stone(s) selected for ELS Treatment. This study requires one additional ELS Treatment to be performed if needed, as discussed in the section above. These additional stone interventions will be recorded on the appropriate eCRF. Adverse events will be assessed using the definitions in Section 8.1.

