6.5 Analysis of collected stone fragments

The collected stone fragments will be characterized by a qualified, central laboratory to determine stone chemical composition. The composition of the stone depends on the substances in the urine causing the stone. It may be made of just one chemical compound or have different chemicals in different layers. The analysis will be done in order to help identify the chemical composition of the stone, which in turn may guide better treatment options for participants with recurrent stone formation.

Table 2: Schedule of Events

Assessment	Screening	ELS Treatment	Days 1,2, and 3 after each ELS procedure	Day 7 (+/- 1) day after each ELS procedure	Day 14 (+/- 4) days after each ELS procedure	Day 30 (+/-4) days after last ELS procedure	Day 90 (+/-21) days after last ELS procedure
Site Visit	✓	✓	By telephone	By telephone	✓	✓	✓
Informed Consent	✓						
Inclusion / Exclusion criteria	✓						
Medical History	✓						
Pregnancy test	✓						
Physical Exam	✓				✓	✓	✓
Serum Creatinine	✓					✓	✓
Urinalysis and urine culture	✓				✓		
CT scan (non-contrast)	✓ (within 14 days of ELS)					✓	
X-ray (KUB)	✓ ¹				✓		
Ultrasound (renal bladder)					✓		✓
2 nd ELS Treatment Eligibility					✓ ²	✓ ²	
Participant urine straining, retaining stones for office visit		✓	✓	✓	✓	✓	
AE reporting		✓	✓	✓	✓	✓	✓
Complete Pain Questionnaire	✓ (within 1 day of ELS)		✓	✓	✓	✓	
Concomitant Meds (analgesics, alpha blockers, pain meds etc.)	✓	✓	✓	✓	✓	✓	✓
Complete Participant Satisfaction questionnaire						✓	
1: Recommended for participants suspected of having radiolucent stone(s) if CT scout film not available for use.							
2: ELS procedure repeated if CT scan shows stone/fragments of 3mm or more.							

Confidential

Page 20 of 1

Study of an Enhanced Lithotripsy System in the Treatment Of Urinary Stone Disease (STONES)

Version 2.0, July 10, 2019

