11. STATISTICAL METHODS

11.1 Population to be analysed

Primary analyses of study data will include available data on all enrolled participants, referred to in International Conference on Harmonization document E9 (“Statistical Principles for Clinical Trials”) as the full analysis set. Study enrollment is defined as that time when the participant signs the informed consent form and is then eligible to begin screening assessments. Other study participants will be classified as screen failures.

Study analyses will then be conducted on two distinct cohorts of study participants: an intent-to-treat (ITT) analysis including all enrolled participants and all available data, and a per-protocol (PP) analysis including the subgroup meeting all inclusion and exclusion criteria and for whom treatment was performed according to the study protocol with follow-up through 30 days (or 14 days if no follow-up imaging was required beyond 14 days). Both ITT and PP analyses will be summarized and reported.

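### The protocol is inconsistent on whether the second ELS is required, so the per-protocol set can lose participants not cleared by the first ELS but none cleared by it, which can bias its success rate upward

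*Combined protocol and SAP*

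**What the plan says.** Two places state the second treatment as a requirement. Section 6.4: "This study requires one additional ELS Treatment to be performed if needed", with a reference back to the section above it. Table 2, footnote 2: "ELS procedure repeated if CT scan shows stone/fragments of 3mm or more", with no exception.

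Two places treat it as optional. Section 6.3.1 asks the investigator to document why participants who are eligible for an additional ELS "Treatment but decline, or based upon the investigator's discretion, are not suitable for an additional ELS Treatment". Sections 6.2.5 (Day 14) and 6.2.6 (Day 30) say that, with a residual of 3 mm or more, "the participant is eligible for one additional ELS Procedure".

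Section 11.1 defines the PP set as participants who meet all entry criteria and "for whom treatment was performed according to the study protocol with follow-up through 30 days", or through 14 days if no imaging was required after that. It does not say whether a missed second ELS means that treatment departed from the protocol. The same section puts the main analysis elsewhere: "Primary analyses of study data will include available data on all enrolled participants". ITT and PP results are both to be reported, and no precedence between them is given.

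Section 11.3 defines success as no stone, or fragments under 3 mm, on imaging through the 30-day visit after the last ELS, following at most two treatments. The test passes if the exact two-sided 95% lower limit exceeds 0.50.

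**The concern.** Take a participant with a residual of 3 mm or more after the first ELS who declines the second, or who goes on to another procedure. Under section 6.4 and the footnote, treatment was not completed as the protocol requires, and the participant can be left out of PP. Under section 6.3.1, the participant followed a course that the protocol foresees and stays in. A participant cleared by the first ELS needs no second and cannot be removed by this route. PP membership can therefore depend on the result of treatment.

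The follow-up condition can reach the same people. The on-site visit item in section 6.2.6 names two cases: a successful first treatment, or a second treatment performed. It has no branch for an unsuccessful first treatment with no second. The heading of section 6.2.6 (after each procedure) and Table 2 (after the last procedure) still schedule a 30-day CT for this participant. If follow-up in practice stops after a switch to another intervention, however, the participant fails the PP follow-up condition.

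What is at stake is the credibility of the PP result. It will be reported beside ITT in a single-arm study whose data are meant to support premarket applications (section 2.2). In an open study, the choice between the two readings could be made after outcomes are known.

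**Working it through.** **Inputs from the protocol (sections 11.3 and 11.6).** Performance goal 0.50; assumed ELS success 0.68; 58 evaluable; two-sided alpha 0.05; minimum passing result 37/58.

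**Inputs assumed, because the documents give none.** True overall success of exactly 0.50; first-ELS success s of 0.35 or 0.40; fraction u of first-treatment failures not retreated, from 0.05 to 0.30; every un-retreated participant is a failure on the endpoint and is dropped from PP.

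**Step 1, the plan's own figures.** The exact (Clopper-Pearson) lower limit for x successes in n is the 0.025 quantile of Beta(x, n − x + 1).
- 37/58 gives 0.501 (the plan states 0.502; the decision is the same). 36/58 gives 0.484. The pass mark of 37 is confirmed.
- P(X ≥ 37) for Binomial(58, 0.68) is 0.7975, so the planned 80% power is reproduced.
- P(X ≥ 37) for Binomial(58, 0.50) is 0.0240. This 2.4% is the reference when all 58 are kept.

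**Step 2, how few removals change a result.**
- 36/58 = 62.1%, limit 0.484, misses the goal. Without two failures, 36/56 = 64.3%, limit 0.504, clears it.
- 33/58 = 56.9%, limit 0.432, misses. Without seven failures, 33/51 = 64.7%, limit 0.501, just clears it.

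**Step 3, chance that PP clears the goal when true success is 0.50.** The share of all treated participants who are dropped is (1 − s)u. The PP success probability is q = 0.50 / [1 − (1 − s)u]. The PP size is n = 58 × [1 − (1 − s)u], rounded. The chance of passing is P(X ≥ pass mark) for Binomial(n, q).

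| s | u | n | q | Pass mark | P(PP passes) |
|---|---|---|---|---|---|
| 0.35 | 0.05 | 56 | 0.517 | 36 | 0.039 |
| 0.35 | 0.10 | 54 | 0.535 | 35 | 0.062 |
| 0.35 | 0.20 | 50 | 0.575 | 33 | 0.140 |
| 0.35 | 0.30 | 47 | 0.621 | 31 | 0.351 |
| 0.40 | 0.05 | 56 | 0.515 | 36 | 0.037 |
| 0.40 | 0.10 | 55 | 0.532 | 36 | 0.045 |
| 0.40 | 0.20 | 51 | 0.568 | 33 | 0.160 |
| 0.40 | 0.30 | 48 | 0.610 | 32 | 0.257 |

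This gives about 4-6% for u of 5-10% and about 14-35% for u of 20-30%. Letting the number removed vary at random, instead of fixing n, changes the upper range to about 13-33%. If un-retreated participants stay in PP as failures, the figure returns to 2.4%.

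**The case against.** The best case against this point is textual. The sentence in section 6.4 refers back to the section above it, which contains the provision for declining or being judged unsuitable. The sentence before it accepts that other interventions may be needed, section 6.3.2 only recommends the timing of a second treatment, and the endpoint allows at most two treatments, so one is a valid course. On this view, a documented refusal is within the protocol and the participant stays in PP. Section 11.7 also defers detail to a separate SAP, which could settle the matter. This stands in part: exclusion is one reading, not a stated rule. Footnote 2 carries no exception, though, and section 11.1 does not choose between the readings.

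A reader might infer three stronger things that the documents do not support.
- **That un-retreated participants do fall out of PP.** No section says so.
- **That all of them are endpoint failures.** A residual seen at Day 14 may have passed by the Day 30 CT, which would meet the success definition. Nor does any section say how clearance by a non-ELS procedure counts; section 6.4 only has it recorded.
- **That the trial's type I error is inflated.** The primary analysis covers all enrolled participants, and PP has no success rule of its own. The percentages in the table describe the PP result only, and ITT reported beside it would show a discrepancy.

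It is also fair to say that the size depends on the assumptions. At 20-30% un-retreated, between 24% (0.60 × 0.20 / 0.50) and 39% (0.65 × 0.30 / 0.50) of all final failures are removed. At 5-10% the effect is small.

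**Conclusion.** The point holds in a limited form. The documents conflict on whether the second ELS is required, and section 11.1 leaves PP membership open for exactly those participants whom the first ELS did not clear. On the 'required' reading, or where follow-up ends after a switch to another intervention, the PP rate can be biased upward. The harm is confined to PP.

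Removing two failures is enough to move 36/58 across the goal. The chance of a PP result above the goal at a true rate of 50% runs from about 4% to about 35% over the assumed range, against 2.4% with everyone kept. It rests on assumed first-ELS success and un-retreated fractions and on treating all those removed as failures. To the extent that some would have cleared by Day 30, the bias is smaller.

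**What to change.** 1. Reconcile sections 6.3.1 and 6.4 and Table 2 footnote 2 on whether the second ELS is required or optional. Which clinical rule applies is for the sponsor and investigators; this review takes no position on it.
2. State in section 11.1 or the SAP that not receiving a second ELS (declined, judged unsuitable, or a non-ELS intervention instead), and any missing follow-up that results from it, is not a reason for exclusion from PP.
3. State that these participants are scored at the 30-day imaging after their last ELS. They count as failures if a residual of 3 mm or more remains at that imaging, if a non-ELS intervention on the treated stone came before it, or if that imaging is missing after a documented residual of 3 mm or more. A participant who clears without intervention by that imaging remains a success.

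The last two failure conditions go beyond what section 11.3 now says, so they should be written as endpoint rules. Using them in the all-enrolled analysis too would keep the two results comparable.

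The cost is a few sentences and a somewhat lower PP success rate than the 'required' reading would give. No new data are needed, because section 6.3.1 already has the circumstances documented and section 6.4 already has other interventions recorded.
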